Polysomnography (PSG): Continuous and simultaneous recording of physiological variables during sleep, i.e., EEG, EOG, EMG (the three basic stage scoring parameters), EKG, respiratory air flow, respiratory excursion, lower limb movement, and other electrophysiological variables will be used to record sleep during all admissions for subjects. EEG as recorded by the Powersleep device or the standard PSG EEG channels

will also be analyzed for slow wave activity; a measure of the frequency and amplitude of slow waves.

PowerSleep Prototype 1: A wearable and non-invasive device, consisting of a headband with 2 electrodes (one forehead and one mastoid) and speakers located in the headband over each ear. The headband is adjusted via an adjustable slider. The device also includes a right mastoid reference electrode. EEG will be recorded by the PowerSleep device. Soft audio tones (below 65dB) will be administered via the speakers system during deep sleep as determined by the functionality of the device. This PowerSleep device has been extensively studied, and is a released product available for sale. The low risk PowerSleep device does not require a 510(k) and is considered a general wellness medical device.

Prototype 2: The PLL set up will function similarly to the PowerSleep prototype 1, but the stimulation will be provided using a standard PC setup at the bedside using standard PSG electrodes. EEG will be monitored and SWS identified using a standard PSG channels (international 10-20 system: Fpz, F3, F4, C3, C4, P3, P4, O1, O2) referenced to left mastoid. Electro-oculogram (EOG) will be recorded using 2 electrodes placed lateral to each eye and chin electromyogram (EMG) was recorded using 3 chin electrodes. The full EEG data set will be collected using Brain Vision Recorder software (Brain Products GmbH) and stored for off-line analysis and sleep scoring. A Matlab script (R2014b, MathWorks, Natick, MA) was developed for online detection of slow-waves and to control acoustic stimulation in a phase-locked manner (targeting the up phase of the slow wave) as described previously (Santostasi et al., 2016). Acoustic stimulation provided by headphones with an audible soft volume that do not result in arousals will be used. This device has been studied, however, is not a released product and therefore considered investigational.

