- B. Study Participants:** We will enroll up to 60 individuals in order to complete a total of 10 participants using a cross over design. We will recruit male and female participants who satisfy the inclusion and exclusion criteria outlined in the following sections.
- C. Study-wide recruitment methods:** Potential participants will be recruited predominantly through media advertisements (ex. local newspapers, flyers, online advertisements), institutional postings, or existing online communities or site databases of patients who have previously indicated an interest in participating in research.

[name] (Principal investigator) will not be involved in recruiting or consenting research participants, or in data collection. [name] (Co-Principal Investigator) will be responsible for these aspects of the study.

- D. Setting:** Subjects will be identified from the population of prior research subjects who have agreed to be contacted for additional research experiments. New

subjects will be recruited from the general population through use of flyers/posters and online advertisements.

- E. Randomization:** An EDC will be used to control the randomization schedule. This EDC will be set-up by Philips Respironics. The Philips Prototype will be double blind, as neither the study participants, nor study staff will know which is active or sham. The Northwestern Prototype will be single-blind, however scoring will be blinded. If any Serious Adverse Events or Unanticipated Device Effects occur the study staff will alert the sponsor and the sponsor will break the blind if necessary. The study staff will alert the sponsor prior to any unblinding.

IV. INCLUSION AND EXCLUSION CRITERIA

Inclusion Criteria

- Able to provide written informed consent prior to admission
- Able to read, write and speak English
- Adult volunteers aged 21-50
- Working full time (M-F) schedule [Note: Full time is considered a 32 hour work week start time at 7am or later] or full time student
- Self-reported regular sleep schedule who are able to maintain their sleep schedule during the course of the study
- Self-reported sleep latency \leq 30 minutes
- Self-reported wake after sleep onset \leq 30 minutes
- Participants who regularly (3 of 5 work/school nights) use an alarm clock during the work/school week and who self-report:

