The subject will be allowed to go home or to work during the day and will be instructed not to nap during the day. This will be monitored with the actigraph. The subject will return to the lab the following evening 3 hours before the usual bedtime and will be instrumented and studied as described for night 1. For example, participants that spent the night Monday and completed Tuesday morning testing will come into the lab Wednesday night for Thursday morning testing or if participants spent Tuesday night and completed Wednesday morning testing they will come into the lab Thursday night for Friday morning testing.

Visit 4 Procedures (3 days/2 nights):

Participants will return to the Sleep Disorders Center to complete the second set of overnight studies one or two weeks after the first set of overnight studies. If participants spent Monday and Wednesday night in the lab for the first set of overnight studies, they will complete the second set of overnight visits Monday and Wednesday. The actigraph data will be similarly downloaded and reviewed for further participation upon arriving at the Sleep Disorders Center. This visit will be identical to Visit 3 except that the subjects will receive the prototype system that was not used in Visit 3 (Prototype 1 or 2).

V. STATISTICAL ANALYSIS

Determination of Sample Size

Twelve participants will be enrolled in order to ensure ten completed data sets. Since this is a pilot study, no sample-size calculation was performed.

General Considerations

The primary analysis will be performed including all completed participants. Subjects who complete all 4 in lab study nights with functional devices will be included in data analysis. If the sleep data are not usable for one or more of the participants' treatment conditions, those participants will be excluded from the primary analysis, and site(s) may over-enroll to compensate for these missing data. The analysis of safety will include all randomized subjects.

All variables will be summarized by descriptive statistics. The statistics for continuous variables includes mean, median, standard deviation, minimum, maximum, 95% confidence interval (CI) for the mean, and number of observations. For categorical variables, number and percentage of subjects with the event will be presented. Continuous variables will be summarized using the number of non-missing observations,

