mean, standard deviation (SD), 95% confidence interval (CI) for the mean, median, minimum, and maximum; categorical variables will be summarized using the frequency count and the percentage of subjects in each category. All analyses will be conducted using either SPSS® or SAS® software.

There are no statistical criteria for terminating the study. No sensitivity analysis will be completed, and any deviations to the original statistical plan will be noted in the analysis report.

Philips Respironics will complete the data analysis on Prototype 1. In addition Philips Respironics will analyze the Prototype 2 data in the same manner.

Subject Disposition

Subject disposition, including the total number of participants enrolled, randomized, completed, early terminations and withdrawals, will be presented by treatment group, and overall. In addition, a listing will be provided with the reasons for discontinuation by treatment group.

Demographics and Baseline Characteristics

Standard subject demographics (e.g., age and gender) and baseline characteristics will be summarized for all participants enrolled and for evaluable subjects.

Treatment Compliance

It is expected that the drop-out rate will be low as the study is of short duration and will be completed in a controlled, in-lab setting.

Primary Efficacy Analysis

The primary efficacy measure for this study is the cumulative or average slow-wave activity (SWA).

The primary analysis will be done on completed participants with SWA data collected during the four conditions: Prototype 1 active and sham, Prototype 2 active and sham. A 2-way repeated measures Analysis of Variance (RMANOVA) will examine the SWA data with the repeated measures factors of therapy (active and sham) and prototype (1 and 2). An interaction factor will also be included to determine whether the active / sham effect differs between prototypes. The significance level will be $p < 0.05$.

If the required assumptions for the RMANOVA model are violated, transformation of the data or non-parametric procedures may be used.

Secondary Efficacy Analysis

The daytime outcomes will be analyzed using the same statistical model as the SWA data.

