All adverse events, serious and non-serious, occurring during the course of the study will be collected, fully documented, and reported to the Northwestern University Internal Review Board (IRB) and to the Sponsor by the Principal Investigator, [name] or designee. Serious adverse events will be reported to the Sponsor within 24 hours of the study team being aware of the event. For each adverse event, the investigator will provide the onset, duration, intensity and treatment required, outcome and action taken. We anticipate that adverse events during this study would be related skin irritation from PSG or sleep deprivation from acoustic stimulation. All reasonable care will be taken to avoid these complications. In addition to adverse event reporting, the investigators will report a summary of the protocol findings, subject recruitment, drop-outs, and events to the IRB annually. The physiological studies will be conducted in the Sleep Disorders Center on the 7th Floor of Arkes Pavilion. All data will be kept confidential and in a locked cabinet. Only approved study personnel will have access to study related documents.

All device deficiencies, use or user errors, and equipment failures will be documented. Use or User errors will be captured as part of the source documentation. Device deficiencies and equipment failures will be kept on a separate log. The serial numbers and type of deficiency/failure will be captured. If the deficiency/failure is related to Prototype 1, Philips Resironics Engineering team will be notified to troubleshoot the issue.

This clinical study will be monitored by Philips Resironics Inc. (Sponsor) in compliance with the Code of Federal Regulations (CFR) for clinical research; namely, 21 CFR Parts 50, 54, 56 and 812 and others as applicable. The purpose of such monitoring is to assure that the study remains in compliance with the approved protocol, investigator agreement and regulatory requirements, to verify the completeness and accuracy of study data and

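### The sponsor analyses both its own prototype and another developer's, and nothing in the plan masks active/sham from its analysts or from whoever judges sleep data unusable

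*Combined protocol and SAP*

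**What the plan says.** **Who controls allocation.** Section III.E (Randomization) states "An EDC will be used to control the randomization schedule" and then "This EDC will be set-up by Philips Respironics". The same section lets the sponsor break the blind if a serious adverse event or unanticipated device effect requires it. Section VII identifies the same company as sponsor and monitor.

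**Who analyses.** Section V, General Considerations, gives the sponsor the Prototype 1 analysis and continues: "In addition Philips Respironics will analyze the Prototype 2 data in the same manner". Section III.E calls Prototype 1 the Philips prototype, and its definition says it "is a released product available for sale". Section I says Prototype 2 was developed at Northwestern. Comparing the two is part of the primary aim in Section II and is tested by the interaction term in the Primary Efficacy Analysis.

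**Who is blinded.** For Prototype 1, participants and study staff. For Prototype 2: "The Northwestern Prototype will be single-blind, however scoring will be blinded". Visit 2 Procedures confirms that study staff know the condition on Prototype 2 nights.

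**What is left open.**
- If sleep data from any condition cannot be used, "those participants will be excluded from the primary analysis". No criterion and no decision-maker is given.
- The primary measure may be cumulative or average SWA.
- The polysomnography definition takes SWA from the device or the standard channels. The SWA definition names both.
- A transformation or a non-parametric method may be used if model assumptions fail.
- General Considerations rules out sensitivity analyses.
- An interim analysis follows 5 to 6 completers, without saying who sees condition.

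**The concern.** Cleaning the EEG, accepting or rejecting a night, choosing the SWA measure and its source, and choosing the model all come before the primary test. If the people making these choices can see which nights were active, the choices can drift towards a result without any intent. Two features make this matter more here. The analysing party has an interest in one of the two systems compared, and with 10 completers a single exclusion carries weight. With no sensitivity analysis planned, nothing in the report would show whether a particular choice drove the finding. What is at stake is whether the active/sham effect, and the comparison between prototypes, can be defended to a sceptical reader.

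**Working it through.** **Text check: does any provision close the gap?**

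1. *Blinded scoring (III.E).* It is stated for Prototype 2 only. The Sleep Quality definition uses scoring for sleep stages, while the SWA definition speaks of analysing. The natural reading is blinded sleep staging. That protects the nonREM epochs entering SWA, but not artefact handling, EEG source, SWA measure, usability or model.
2. *Anonymous analysis by study number (VI, Confidentiality).* This hides identity, not active/sham.
3. *Staff blinding (III.E; Visit 2 Procedures).* It covers study staff on Prototype 1 nights only. The sponsor's analysts are not mentioned.

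None of the three blinds the analysts or the usability decision.

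**Illustration of size.** The plan has no sample-size calculation and no SD for SWA change, so there is no figure to reproduce and the SD must be assumed.

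*Shift in SD units.* The expected minimum of 10 independent standard normal values is −1.54.
- Dropped, not replaced: the mean of the other nine rises by 1.54/9 = 0.171 SD.
- Dropped and replaced by a random participant (General Considerations and Withdrawal Criteria allow over-enrolment or replacement to reach 10): 1.54/10 = 0.154 SD.

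*Assumed SD, first route.* Section I reports that 18/24 (75%) had an SWA increase above 0% and 15/24 (62.5%) above 5%. Under normality, mean/SD = 0.674 and (mean − 5)/SD = 0.319, so SD = 5/(0.674 − 0.319) = about 14.1 points. Moving one person in the second count gives about 10.8 (14/24) or 20.5 (16/24).

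*Assumed SD, second route.* The 6.2% mean increase in the 28-person pilot combined with the 75% from the other study gives 6.2/0.6745 = 9.2 points. This mixes two studies.

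| Case | SD 9.2 | SD 14.1 |
|---|---|---|
| Not replaced (0.171 SD) | 1.6 | 2.4 |
| Replaced (0.154 SD) | 1.4 | 2.2 |

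Against the 5% in Section II, the range is 1.4/5 = 28% to 2.4/5 = 48%.

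*Prototype comparison.* Exclusion removes a participant from all four conditions. If the person dropped is the least favourable on one prototype, and the two changes have equal SDs and correlation ρ (bivariate normal), the other prototype's mean also moves, by ρ × 0.171 SD. The difference between prototypes then moves by (1 − ρ) × 0.171 SD. The documents give no value for ρ, so this shift is not quantified.

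**The case against.** The case on the other side has substance.

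- **Roles.** No one is named as deciding usability, and the sponsor is given data analysis only. The sponsor sets up the data-capture system; the text does not say it writes the schedule, or that the system's administrator and the analyst are the same person. The seller of Prototype 1 is not named, so a commercial interest is a close inference. All of this stands.
- **Safeguards already present.** Visit 2 Procedures allows a repeat night when data cannot be analysed for technical or environmental reasons. Departures from the plan are to be noted in the report. A change of method is conditional on violated assumptions. Both prototypes are to be analysed alike, and SWA is a spectral quantity (0.5–4 Hz), not a rating. These narrow the room for judgement. They do not mask condition, and an open choice between two permitted options is not a departure that would be reported.
- **Magnitude.** Removing the worst responder because of the outcome would be misconduct, so the figure is an upper illustration for one exclusion and not an expected bias. This stands.
- **Pilot status.** This limits severity. The plan nevertheless tests at p < 0.05 and compares two developers' systems.

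A reader might infer that the sponsor's analysts will work unblinded, or that the comparison would not be credible even if every decision were honest. The documents support neither. They leave unblinded processing possible without saying it will happen, and nothing in them measures the effect of honest decisions.

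**Conclusion.** The gap is real and worth closing. The party that sets up the randomisation system also analyses both prototypes, one of them its own, and no provision keeps its analysts, or whoever judges usability, blind to active/sham. Combined with the open choices and the absence of sensitivity analyses, this means the result could not be shown to be free of analyst influence.

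The size is illustrative: 0.154 to 0.171 SD for the most selective single exclusion, about 1.4 to 2.4 percentage points. It rests on independent, normally distributed changes in 10 participants and on two fragile SDs taken from the background section. The textual finding does not depend on these figures. It is a should-fix point for a pilot, and not evidence that any decision has been or will be biased.

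**What to change.** Add to Section V, General Considerations:

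1. EEG cleaning, night and participant usability decisions, per-night SWA, the choice of SWA measure and EEG source, and the choice of model are made on files with tone markers removed and condition shown only as masked codes (A/B within prototype), then locked and dated. Codes are needed because deleting the labels altogether would leave no therapy factor for checking model assumptions.
2. A sponsor person outside the analysis team holds the key and releases it only after the lock.
3. For the interim analysis, the processing rules, SWA measure and model are locked before any interim unblinding. Usability decisions for the interim participants are locked before their key is released. Later participants stay masked until the final lock.

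The cost is some extra data handling and SAP wording, with no added nights or participants. Masking will be imperfect: the prototype is recognisable from the recording, and evoked responses to tones may hint at condition. Direct knowledge of allocation would still be removed from the decisions that precede the test.

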Psychomotor Vigilance Testing – Brief (PVT-B): The Psychomotor Vigilance Task is a sustained-attention, reaction-time task that measures the speed with which participants respond to a visual stimulus. Sleep loss induces reliable changes in PVT performance, causing an overall slowing of response times, a steady increase in the number of errors of omission (i.e., lapses of attention, usually defined as response times ≥ 500 ms), and a more modest increase in the number of errors of commission (i.e., responses without a stimulus, or false starts) (Basner and Dinges, 2011; Van Dongen et al., 2003). Typically the PVT is a 10 minute assessment but a shorter 3 minute version (PVT-B) has recently been validated in controlled laboratory studies on total and partial sleep deprivation (Basner et al., 2011). The PVT results will be assessed for number of lapses, number of anticipations, average reaction time, average speed, average 10% fastest reaction time, and average 10% slowest reaction time.

Samn-Perelli 7-pt scale: The Samn-Perelli is a 7 point scale which measures subjective levels of alertness. This scale ranges from fully alert, wide awake to completed exhausted, unable to function effectively.

Sleep Quality: Sleep stage distribution will be scored from the standard sleep staging channels. It will also be assessed subjectively using a Visual Analog Scale (VAS) for sleep quality.

Sleep restriction: is also known as chronic sleep deprivation, and exists when the individual routinely sleeps less than required for optimal functioning.

Slow Wave Activity: EEG as recorded by the Powersleep device and the standard EEG channels will also be analyzed for slow wave activity; a measure of the frequency and size of slow waves.

I. BACKGROUND AND SIGNIFICANCE

Sleep disturbances are common in the general population and represent a major public health concern because of health care utilization, medical comorbidities impact on quality of life, and safety (Walsh 2004). In addition to sleep disorders such as insomnia, recent surveys suggest that a large percentage of the population is sleep restricted, and that the impairments in daytime functioning due to sleep restriction are responsible for decreased work productivity, morbidity and mortality related to automobile crashes and other adverse events (Banks and Dinges 2007).

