Methods of sleep modification include pharmacological treatments, behavioral therapy, and homeopathic approaches. Pharmacological sleep aids are limited by side effects and drugs capable of affecting sleep maintenance, despite objective evidence of increased quantity or subjective reports of improved sleep, often have residual next-day effects that overlap with the disease symptoms (Rosenberg 2006). Behavioral and cognitive therapies have also been proven to be beneficial; however, they rely heavily on availability, patient motivation and practitioner skill. Homeopathic solutions are numerous and varied, but one example is the use of melatonin to augment sleep. There is limited evidence of their effectiveness or safety.

There is a need for new ways to improve sleep quality. Recently, researchers at the University of Wisconsin, Northwestern and other locations internationally have found that auditory stimulation can enhance slow wave activity during the night, relative to those times when there is no stimulation. An initial prototype, the PowerSleep System Prototype, was developed to monitor EEG and provide stimulation tones during slow wave sleep. In an initial feasibility trial, auditory stimulation provided by the PowerSleep System Prototype was shown to increase slow wave activity in sleep restricted adults.

A pilot study with 28 participants (average age 37.0 ± 7.3 , 18 female/10 male), was conducted by Philips Respironics. The study showed that it is possible to enhance slow wave sleep by using non-pharmacological methods such as auditory stimulation (AS) and that coupled with closed-loop brain activity monitoring (EEG) provided by the device provides an increase in slow wave activity by 6.2% which may help improve vigilance,

cognitive functions, and memory, as well as subjective ratings of sleepiness, physical fatigue, and mental tiredness.

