As a second test condition of this protocol, we will also utilize a different system, Phase Locked Loop (Prototype 2) to provide acoustic stimulation during sleep. This Phase locked Loop (PLL) system was developed at Northwestern University and functions similarly to the PowerSleep Prototype 1, but the stimulation will be provided using a standard PC setup at the bedside using standard polysomnography (PSG) electrodes and acoustic stimuli will be delivered through earphones at specified times during sleep to increase slow wave activity.

II. SPECIFIC AIMS/HYPOTHESES

Primary Aim:

The primary aim of this study is to assess the effects of the auditory stimulation delivered by both the PowerSleep systems (Prototype 1) and a system developed

by Northwestern University (Prototype 2) in adults with mildly sleep restricted schedules.

We hypothesize that one night of in-lab use of a PowerSleep system (Prototype 1) or Prototype 2 under an active condition (tones played to increase slow-wave activity), as compared to one night of in-lab use of the same PowerSleep system (prototype 1) or Prototype 2 under a sham condition (no tones played) will result in a significant increase ($\geq 5\%$) in cumulative or average slow-wave activity (SWA) in nonREM sleep across the whole night of sleep compared to sham. NOTE: We will also compare the relative ability of Prototype 1 versus Prototype 2 to increase the magnitude of SWA in sleep.

Secondary Aim:

The secondary aim of the study is to assess the impact of active versus sham PowerSleep Prototype 1 and Prototype 2 systems on measures of daytime function (PAL and PVT-B). The estimated effect of PowerSleep on specific measure(s) of daytime function will be used to help inform the choice of outcomes for future studies.

Exploratory endpoints:

Exploratory endpoints will include analysis of other daytime outcome assessments in relation to SWA.

III. STUDY DESIGN AND METHODS

- A. Design:** This study is a randomized, single-blind, sham-controlled pilot cross-over trial comparing the feasibility, and efficacy of 2 nights of in lab use with active versus sham conditions in adults with sleep restricted schedules. The expected duration of the study for each participant is up to 5 weeks.

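### The primary endpoint is cumulative or average NREM slow-wave activity with no rule choosing one, and the EEG source for it is stated inconsistently

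*Combined protocol and SAP*

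**What the plan says.** **The measure.** Section V, Primary Efficacy Analysis: "The primary efficacy measure for this study is the cumulative or average slow-wave activity (SWA". Section II, Primary Aim, puts the hypothesis as an increase of at least 5% in "cumulative or average slow-wave activity (SWA) in nonREM sleep across the whole night of sleep compared to sham". Neither section says which summary is primary or how it will be chosen. Other elements are fixed: the band is 0.5-4 Hz (Background), the state is NREM and the window is the whole night (Primary Aim). The test is a two-way repeated measures ANOVA at p < 0.05, with factors therapy and prototype and their interaction. Section V also states that no sensitivity analysis will be done and that an interim analysis follows 5 to 6 completers.

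**The EEG source.** The Polysomnography definition takes SWA from "EEG as recorded by the Powersleep device or the standard PSG EEG channels". The Slow Wave Activity definition says "EEG as recorded by the Powersleep device and the standard EEG channels will also be analyzed for slow wave activity". The Primary Efficacy Analysis names no source, channel or reference. For Prototype 1, "The device also includes a right mastoid reference electrode". The montage listed for Prototype 2 is Fpz and "F3, F4, C3, C4, P3, P4, O1, O2) referenced to left mastoid". PSG "will be used to record sleep during all admissions for subjects", so a source common to all four nights exists, but it is not named as the primary one.

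**The concern.** A primary endpoint with two permitted definitions allows two primary answers from the same nights. Read literally, the p < 0.05 test and the 5% hypothesis each get two chances, with no adjustment and no requirement to report the summary that was not used.

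The two summaries part company only through NREM time, and the protocol treats a change in sleep continuity as possible. The section on potential risks says stimulation can fragment sleep, and Section VII anticipates adverse events from stimulation-related sleep deprivation.

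The source question matters for a different comparison. The Primary Aim also asks which prototype raises SWA more. If headband EEG served one prototype and PSG the other, that comparison could pick up a difference in recording site and reference.

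**Working it through.** The plan gives no sample-size calculation, power or SD, so it has no figure of its own to reproduce.

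**1. How far apart the summaries can be**

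Cumulative SWA = average SWA × NREM time, so the active/sham cumulative ratio = average ratio × NREM-time ratio.

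Inputs: the target of 5% (Primary Aim), and the Background's statement that the device "provides an increase in slow wave activity by 6.2" per cent in the 28-participant pilot. The Background does not say whether that figure is average or cumulative, so both readings are shown.

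- If 6.2% is the average: cumulative reaches +5% when NREM time falls by 1 − 1.05/1.062 = 1.13%, and reaches zero when it falls by 1 − 1/1.062 = 5.84%.
- If 6.2% is cumulative: average drops to +5% when NREM time rises by 1.062/1.05 − 1 = 1.14%, and a 6.2% rise in NREM time accounts for the whole effect.
- In minutes, for an assumed 250 to 330 min of NREM sleep: 1.13% is 2.8 to 3.7 min.

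**2. Type I error if either summary may support the claim**

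The therapy main effect in the 2×2 within-subject design is a one-sample t test on each person's active-minus-sham contrast averaged over prototypes. With ten completers it has 9 df. On the log scale, log cumulative = log average + log NREM time. If the change in NREM time is independent of the change in average SWA (assumed), a correlation r between the two summaries implies an SD ratio (NREM time to average SWA) of √(1/r² − 1). Simulated under the null, two-sided 0.05:

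| r (assumed) | SD ratio | either summary significant |
|---|---|---|
| 0.99 | 0.14 | 0.057 |
| 0.95 | 0.33 | 0.066 |
| 0.90 | 0.48 | 0.072 |
| 0.80 | 0.75 | 0.080 |

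**3. How often the summaries would disagree**

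An SD is needed. The Background reports that in a 24-person in-lab study 18/24 (75%) rose by more than 0% and 15/24 (62.5%) by more than 5%. Under normality (an assumption, imprecise at n = 24), SD = 5/(z₀.₇₅ − z₀.₆₂₅) = 5/(0.674 − 0.319) = 14% for one active/sham contrast. Averaged over two prototypes, it is 14/√2 = 9.9% if the two contrasts are independent and 14% if fully correlated. Hence the range of 10% to 14%.

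With a true +6.2% in average SWA, n = 10, r from 0.99 to 0.80 and 100,000 runs per setting, exactly one summary is significantly increased in:

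- about 4% to 23% of trials when mean NREM time is unchanged (lowest at SD 14%, r = 0.99; highest at SD 10%, r = 0.80);
- about 10% to 28% if mean NREM time falls by 2%, a figure chosen only for illustration.

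Power for average SWA alone is about 23% to 40% at these SDs.

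**4. What a mixed EEG source would do**

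Suppose headband power equals g times PSG power for the same sleep, sham power is S on PSG, and both prototypes raise SWA by the same fraction e.

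- Active/sham ratio within a prototype: gS(1+e)/(gS) = 1+e. It is unaffected by g.
- Interaction on raw power: gSe − Se = (g − 1)Se, which is not zero unless g = 1. The prototype main effect shifts as well.
- Interaction on a log or percent scale: log(1+e) − log(1+e) = 0. A constant gain cancels.

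**The case against.** *The measure.* The plan speaks of one primary measure in the singular, so an unfinished drafting choice is as natural a reading as a licence to use either. The inflation is small and arises only under the second reading. Several features limit changes in NREM time: tones are calibrated not to wake the user, they are halted for significant sleep disturbance, participants are woken at their usual time, and an arousal index above 20 ends participation. With equal NREM time the two percent changes are identical. All of this stands and keeps the point modest. None of it selects a measure, and a difference of a few minutes is enough to matter for the 5% criterion.

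*The disagreement rates.* A reader might infer that the summaries would conflict in nearly half of trials. That figure (49%) needs a contrast SD of 5% together with a 2% mean fall in NREM time. The 24-person study in the Background points to a much larger SD, and no section suggests such a fall. At the larger SDs power is low, so part of the remaining disagreement is what any two correlated summaries would show in a small pilot. The simulation also works on the log scale, whereas the plan applies RMANOVA to the SWA data and mentions transformation only if assumptions fail. The rates are therefore indicative.

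*The EEG source.* A reader might infer that the active/sham result is confounded with the sensor, or that mixed sources are intended. The documents support neither. Each active night is compared with a sham night on the same prototype, PSG is recorded at all admissions, and Section V says Prototype 2 data will be analysed in the same way as Prototype 1. What stands is that one definition says *or*, another says *and*, and the primary analysis names no source.

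**Conclusion.** The point holds and should be fixed. Confidence is high that the plan leaves the primary measure unchosen, and lower for the simulated rates.

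The break-evens rest only on the identity between the summaries and the plan's own 6.2% and 5%; the conversion to minutes adds the assumed NREM duration. The type I error range rests on assumed correlations. The disagreement range rests on those correlations, an SD inferred under normality, and a true effect of 6.2%. The two fractions used for the SD would, under the same normality, imply a mean nearer 0.674 × 14% = 9.5%, so combining them with 6.2% is a further assumption.

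The RMANOVA tests for any difference, so the 5% figure affects how the hypothesis is judged, not the p-value. The source inconsistency bears on the prototype main effect and, on raw power, on the interaction. In a ten-completer pilot with no sample-size calculation, the consequence is mainly for interpretation.

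**What to change.** Before any SWA data are analysed, including at the interim, add to the Primary Efficacy Analysis wording to this effect:

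*The sole primary endpoint is average 0.5-4 Hz power over whole-night NREM sleep, from one named PSG derivation and reference, used on all four nights and for both prototypes. If that derivation is unusable on any night, a named backup derivation is used for all four of that participant's nights. Cumulative SWA and SWA from device EEG are secondary. Interim results will not be used to choose the measure.*

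Cumulative SWA would serve equally well if it alone were named. The deadline is the first SWA analysis and not unblinding, because staff are not blinded for Prototype 2. The derivation should be one the site already records on headband nights, since the detailed montage is listed only under Prototype 2. The two definitions should be brought into line with the new text.

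The cost is a few sentences and one check by the site. PSG is already planned at all admissions, so no visit or test is added. The sponsor gives up the choice of measure. A participant with no usable derivation on a night leaves the primary analysis, which is one tenth of the data at ten completers unless the over-enrolment allowed under General Considerations replaces the loss.
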